7.4.3 Accrual

Each site is expected to enroll 50 participants in approximately the first six months during the safety phase of the study. The remaining participants will be enrolled over approximately 24 months. The actual number accrued at each site will be higher at sites anticipated to have higher HIV seroincidence rates, with each site expected to accrue between 200 and 600 participants to achieve the total sample size of 1500. Site accrual targets will be closely monitored and adjusted as needed in response to site performance, while balancing the need to achieve targeted event rates.

Approximately every three months during the accrual period and at the recommendation of protocol team members, the HPTN SMC or the DSMB, the protocol team will review performance data from each study site — including accrual rates, retention rates, protocol adherence measures, data quality measures, and HIV incidence rates — to determine whether enrollment slots should be shifted across sites to achieve the study objectives most efficiently.

7.5 Random Assignment

Participants will be randomized in a 1:1 ratio, with 750 participants in each arm. In an unblinded trial, special care needs to be taken to assure that the study staff cannot control or guess assignment to arm. Techniques such as large block size, and/or dynamic allocation between sites may be used. The HPTN Statistical and Data Management Center will coordinate these procedures, which will be specified in the SSP manual.

7.7 Data Analysis

7.7.1 Primary Analysis

An intent-to-treat analysis will be conducted using the entire sample from all sites. The incidence of HIV-1 and mortality rates will be determined among participants in each study arm. Endpoints will be compared between treatment arms using Kaplan Meier estimates of the proportion uninfected and living by the 104-week visit, with variances estimated by Greenwood's formula.

Since significant loss-to-follow-up results in a risk of bias in the efficacy analysis, our intention is to make considerable efforts to achieve rates of loss-to-follow up that are no more than 10% at two years. In addition, to more fully assess the potential impact of individuals lost-to-follow-up, we plan to conduct a sensitivity analysis where, for each individual in the drug and counseling group who is lost, we will use an imputation of subsequent risk of infection that is based in the estimated subsequent risk of infection in the control arm. This will allow us to gain insight into the potentially optimistic estimation of the efficacy based on imputing risk of infection of those lost to follow-up in the treatment arm with the estimated subsequent risk of those remaining on treatment in the treatment arm.

7.7.2 Secondary Analyses

- 1. To determine if the substitution treatment reduces average HIV incidence and death compared to the detoxification arm; and reduces HIV incidence and death at 52 weeks and 156 weeks.
- 2. To determine if the substitution treatment decreases average HIV incidence compared to the detoxification treatment; and decreases HIV incidence at 52, 104, and 156 weeks.
- 3. To compare the average rates of deaths between the two arms; and the rates of death at 52, 104, and 156 weeks.
 - For each of the above three endpoints, "average" rates will be compared between treatment arms using a log-rank test, which utilizes all the event information accumulated in the trial. Rates will then also be compared for the specified time points using Kaplan Meier estimates of the proportion uninfected after the 52, 104 and 156 week visits, and with variances estimated by Greenwood's formula.
- 4. To compare the self-reported frequency of injection, drug and sex-related HIV risk behaviors in the two study arms.
 - Self reported behaviors will be analyzed using generalized estimating equations techniques for repeated measures of behavior to assess difference in frequency of use between the two study arms.
- 5. To compare the frequency of drug use measured by self-report and by urinalysis in the two study arms.
 - Urinalysis results will be compared between arms using simple cross sectional summaries at each time point, in addition to generalized estimating equation approaches for repeated measures. In addition, comparison between urinalysis and self-reported injection frequency will be used to assess validity of self reported data.

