2.2 Secondary Objectives

The secondary objectives of this study are:

- 1. To determine if the substitution treatment reduces average HIV incidence and death compared to the detoxification arm, and reduces HIV incidence and death at 52 weeks and 156 weeks.
- 2. To determine if substitution treatment decreases average HIV incidence compared to the detoxification arm, and HIV incidence at 52, 104, and 156 weeks.
- 3. To compare the average rates of death in the two arms; and the rates of death at 52, 104, and 156 weeks.
- 4. To compare the self-reported frequency of injection, drug and sex-related HIV risk behaviors in the two study arms.
- 5. To compare the frequency of drug use measured by self-report and urinalysis in the two arms.

In addition, the study will provide an opportunity to assess the feasibility of community-based drug treatment in areas where such treatments are currently unavailable and to identify possible structural and attitudinal barriers to substance abuse and HIV care for IDUs. A review of local

and national laws and legal practices that pose risks of adverse social consequences for drug users and people with HIV will be conducted at baseline and annually at each site.

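### Section 7.7.2 names the Kaplan-Meier proportion uninfected as the fixed-time estimator for all three time-to-event secondary endpoints, but it fits only HIV infection

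*Protocol*

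**What the plan says.** Section 7.7.2 lists three time-to-event comparisons: (1) HIV infection or death, (2) HIV infection, (3) death. For the first it asks whether substitution treatment "reduces HIV incidence and death at 52 weeks and 156 weeks". For the third the aim is "To compare the average rates of deaths between the two arms; and the rates of death at 52, 104, and 156 weeks", which matches secondary objective 3 in Section 2.2.

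One shared paragraph gives the analysis, opening with "For each of the above three endpoints". It has two parts:

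- **Average rates:** "rates will be compared between treatment arms using a log-rank test, which utilizes all the event information accumulated in the trial".
- **Fixed time points, in weeks and with Greenwood variances:** "Rates will then also be compared for the specified time points using Kaplan Meier estimates of the proportion uninfected after the 52, 104 and 156".

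For the primary endpoint, the preceding Section 7.7.1 uses "Kaplan Meier estimates of the proportion uninfected and living by the 104-week visit". Section 7.2.2 lists mortality as a secondary endpoint separate from HIV infection.

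**The concern.** A Kaplan-Meier estimate of the proportion uninfected has infection as its only event, and a participant who dies uninfected is censored. That suits endpoint 2. For endpoint 1 the event-free state is uninfected and living. For endpoint 3 it is living, whatever the HIV status.

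As worded, the fixed-time part therefore gives two of the three endpoints the wrong event. Under endpoint 3, an infected participant who is alive would count as an event and one who dies uninfected would not. Under endpoint 1, deaths at 52 and 156 weeks would be censored, which Section 7.4 says it wants to avoid: it chose HIV-free survival because censoring deaths is informative.

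At stake are the fixed-time results for secondary objectives 1 and 3. They matter because Section 7.6 expects that hazards may be non-proportional, or even cross, once drug stops at 52 weeks. An averaged log-rank comparison then does not replace the time-point contrasts.

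**Working it through.** **1. Event-free state needed and event-free state stated**

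| Endpoint in 7.7.2 | Times asked for | State needed | State stated | Match |
|---|---|---|---|---|
| 1. HIV or death | 52, 156 weeks | uninfected and living | uninfected | no |
| 2. HIV | 52, 104, 156 weeks | uninfected | uninfected | yes |
| 3. Death | 52, 104, 156 weeks | living | uninfected | no |

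No other part of the protocol names a fixed-time estimator for death, or for the composite at 52 or 156 weeks. Section 7.7.1 covers the composite at 104 weeks only.

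**2. The plan's 104-week rates (Section 7.4)**

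- Detoxification HIV risk: 1 − (1 − 0.054 × 0.8)² = 0.0845, stated as 8.5%. Death: 4%. Sum: 12.5%, as stated.
- Substitution: 8.5% × 0.50 = 4.25% for HIV and 4% × 0.75 = 3% for death. Sum: 7.25%, as stated.
- Sample size in 7.4.1: (1.960 + 1.2816)² × (0.125 × 0.875 + 0.0725 × 0.9275) / 0.0525² = 673.3 per arm, about 1347 in total against 1345 stated. It rests on the composite with deaths counted, so the sentence in 7.7.2 does not touch it.

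**3. Endpoint 3 at 104 weeks (detoxification v substitution)**

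- Intended: 4% v 3%, a reduction of 1 − 3/4 = 25%.
- Literal rule: 8.5% v 4.25%, a reduction of 1 − 4.25/8.5 = 50%. This is the HIV result.

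**4. Endpoint 1 at 52 and 156 weeks**

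The plan gives no composite rates at these times, so constant hazards are assumed for illustration. The risk at t years is 1 − (1 − p)^(t/2), where p is the 104-week risk.

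Literal rule (infection only):

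- 52 weeks: 1 − √0.915 = 4.3% v 1 − √0.9575 = 2.1%
- 156 weeks: 1 − 0.915^1.5 = 12.5% v 1 − 0.9575^1.5 = 6.3%

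The intended composite is calculated in two ways, because the plan adds the two components while independent hazards multiply the event-free proportions:

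| Basis | 104-week event-free proportions | 52 weeks | 156 weeks |
|---|---|---|---|
| Independent hazards | 0.915 × 0.96 = 0.8784; 0.9575 × 0.97 = 0.9288 | 6.3% v 3.6% | 17.7% v 10.5% |
| Plan's added composite | 0.875; 0.9275 | 6.5% v 3.7% | 18.2% v 10.7% |

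**5. Limit of step 4**

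The plan does not hold constant hazards. Section 7.6 expects the largest difference at 52 weeks. The first table in 7.4.2 has substitution-arm infection of 1.2% at one year and 3.8% at two years for a baseline of 5 per 100 person-years, so most of it falls after drug stops. The figures in step 4 show direction and rough size and are not forecasts.

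**The case against.** The intent can be recovered. The sentence speaks of rates at the specified time points, and those listed just above it include death rates. Section 2.2 asks for the same: "To compare the average rates of death in the two arms; and the rates of death at 52, 104, and 156 weeks". Section 7.2.2 lists mortality separately, 7.7.1 words the composite correctly, and 7.4 explains why deaths are counted. The sentence is loose in another way too: it lists 104 weeks for all three endpoints, although item 1 asks only for 52 and 156. An analyst would very likely notice the mismatch, and an SAP, not at hand, may define events and censoring for each endpoint. All of this stands and makes an actual miscalculation unlikely. It does not make the sentence right, since this is the only fixed-time rule the protocol gives for these endpoints.

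A reader might infer more in three ways, none of which the documents support:

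- *That the whole secondary time-to-event analysis uses the wrong event.* The log-rank comparison is specified for each endpoint and is not tied to infection. Only the fixed-time comparisons are affected.
- *That mortality will in fact be reported with the HIV effect.* That follows only if the sentence is carried out against the protocol's own objectives.
- *That a fixed share of composite events would be lost at 52 weeks.* Any such percentage rests on constant hazards, which 7.6 does not expect.

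**Conclusion.** The point holds as a minor wording error in the fixed-time sentence of 7.7.2. The stated estimator is right for HIV infection, and wrong for death and for the composite at 52 and 156 weeks. It conflicts with 7.7.1 and with the rationale in 7.4.

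For death at 104 weeks, the size of the literal error follows directly from the plan's rates, as in step 3. For the composite it rests on the constant-hazard illustration in step 4 and should be quoted only as a range with that caveat. The primary endpoint and its estimator, the sample size, the one-sided alpha of 0.025 and the log-rank comparisons do not depend on the sentence. It is probably a drafting slip, but correcting it now is better than leaving the event to be inferred at analysis in an open-label trial.

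**What to change.** Replace the fixed-time sentence in 7.7.2 with Kaplan-Meier estimates and Greenwood variances specific to each endpoint:

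- **Endpoint 1 (HIV infection or death):** proportion uninfected and living at 52 and 156 weeks.
- **Endpoint 2 (HIV infection):** proportion uninfected at 52, 104 and 156 weeks.
- **Endpoint 3 (death):** proportion living at 52, 104 and 156 weeks, regardless of HIV status and including deaths after infection.

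The cost is one sentence. It needs no new data, no additional analysis and no change to sample size or alpha.

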5.0 STUDY PROCEDURES

An overview of the study procedures schedule is presented in Appendix I A and B. Participants randomized to the detoxification arm will be expected to complete approximately 45 to 60 visits (depending on whether or not a second detoxification is required) throughout the first year in the trial, while those in the substitution treatment arm will complete approximately 155-160 visits. The greater number of visits in the substitution treatment arm is due to three times weekly BUP/NX dispensing visits. Detailed instructions to guide and standardize all study procedures across sites will be provided in the SSP manual.

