5.3.1 BUP/NX Dispensing Visits

Participants will come to the study site for BUP/NX administration routinely for the appropriate number of weeks, depending on randomization assignment, as described in Section 4.3.3. Study staff will determine with the participant the optimal routine schedule and will carefully explain the procedures for drug administration. Efforts will be made to make these visits as quick and convenient as possible to minimize participant burden and maximize adherence. Dispensing visits can be combined with counseling and follow-up visits.

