5.3.2 Drug and Risk-Reduction Counseling Visits

At the enrollment visit, participants will be scheduled for the 12 weekly counseling sessions as described in Section 4.1. Approximately every four weeks, participants will be asked to provide urine for drug testing during the counseling visits for the first year of enrollment. Women will have pregnancy testing approximately every four weeks during counseling visits for those in the substitution arm, and only at the fourth week and again approximately four weeks after the second detoxification if conducted for women in the detoxification arm.

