5.3.3 Monthly Counseling Sessions

Monthly counseling sessions will be scheduled approximately every four weeks beginning at week 16 through week 52. Refer to Section 4.2.2 for a description of sessions. At each of these sessions, participants will be asked to update their locator information and provide urine for drug and pregnancy testing (for women in the substitution treatment arm only). Monthly counseling sessions can be combined with dispensing and follow-up visits.

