5.5 Assessments During Full Study

In addition to intervention and laboratory visits, participants will be asked to come to the clinic every six months for clinical assessments including HIV testing and urine testing for opiates and other drugs. The week 24 counseling visit and the Week 26 follow-up visit may be combined into one visit to reduce participant visit burden. There should be no duplication of any laboratory test or the collection of any study information if the visits are combined. Visits will also include a behavioral assessment of HIV-related drug and sexual risk. More detailed assessments will be performed for all participants during the treatment phase of the study. The procedures for each visit are described below. Follow-up visits can be combined with monthly counseling sessions and BUP/NX dispensing visits.

ALT and bilirubin testing also will be performed at weeks 12 and 40 for all participants (in addition to tests completed at regularly scheduled follow-up visits); this blood draw will occur at the same visit as the urine test and counseling visit. Whenever clinically indicated, hepatitis B or C testing may be done by the study clinician.

Locator information will also be assessed at four-week intervals. To the extent possible, site staff will work with the participant to determine the best day of the week and time for this visit to be conducted each week (e.g., every Monday at 9 am). The counseling schedule will coincide with a BUP/NX dispensing visit, if possible, to minimize participant burden. Counseling visits may also be combined with follow-up visits.

5.5.1 26 and **52** Week Visits

These visits will include:

- Locator information update
- Symptom-directed physical exam, interim medical history
- Hematology (CBC, platelet count)
- Blood chemistry (creatinine)
- Liver function tests (ALT, bilirubin)
- Hepatitis testing (Week 26)
- Administer HBV vaccine if appropriate
- Urine testing for opiates and other drugs
- Pregnancy urine test for women in substitution arm and women in the detoxification arm who are undergoing a second induction
- Risk assessment (sex and drug use)
- Rapid HIV testing with pre- and post-test counseling
- Social harms assessment
- Intervention acceptability assessment

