7.2.2 Secondary Endpoints

Consistent with the secondary study objectives, the following endpoint(s) will be assessed:

- 1. HIV-1 infection every six months at scheduled study follow-up visits
- 2. Mortality
- 3. Continued opiate use as measured by self-report and urinalysis
- 4. Self reported frequency of injection
- 5. Self reported frequency of injection with previously used injection equipment (needles, syringes, cookers, cottons, and rinse water).
- 6. Self-reported frequency of unprotected sex or sex sold/traded for drugs

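### Most year 1 urines depend on counseling attendance, which dispensing supports mainly in one arm, and the named comparison states no weighting or imputation for missing specimens

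*Protocol*

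**What the plan says.** The endpoint is listed in Protocol 7.2.2 as "Continued opiate use as measured by self-report and urinalysis". The analysis in 7.7.2 item 5 reads: "Urinalysis results will be compared between arms using simple cross sectional summaries at each time point, in addition to generalized estimating equation approaches". It gives no denominator and no rule for specimens that were not obtained. The one missing-data sensitivity analysis, in 7.7.1, imputes risk of infection and does not touch urine results.

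On collection, 5.3.2 says: "Approximately every four weeks, participants will be asked to provide urine for drug testing during the counseling visits for the first year of enrollment". For weeks 16 to 52, 5.3.3 adds: "At each of these sessions, participants will be asked to update their locator information and provide urine for drug and pregnancy testing". Urine is also taken in both arms at the assessments at weeks 26, 52, 78, 104, 130 and 156 (5.5.1, 5.5.2, Appendix I-A).

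On reasons to attend, 5.3.1 says: "Dispensing visits can be combined with counseling and follow-up visits", and 5.5 asks that counseling coincide with dispensing where possible. Section 2.3 limits drug in the detoxification arm to 18 days, with a possible repeat at 26 weeks; the substitution arm is dosed to week 52. Section 5.0 expects about 155-160 year 1 visits in the substitution arm and 45 to 60 in the detoxification arm, and explains: "The greater number of visits in the substitution treatment arm is due to three times weekly BUP/NX dispensing visits".

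**The concern.** Cross-sectional summaries and GEE, applied as named, use the specimens that exist. Unweighted GEE is in general valid only if specimens are missing completely at random, or if missingness depends only on covariates in the model, such as arm and visit. It does not correct for missingness that depends on drug use itself.

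The schedule makes such dependence plausible and gives it a reason to differ by arm. A substitution participant still being dosed is at the clinic anyway when a urine falls due. A detoxification participant past day 18 comes for counseling. A substitution participant who has stopped the drug also loses the dispensing reason, and may be more likely to have relapsed. These mechanisms can push the arm difference either way.

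At stake is the laboratory measure of whether substitution treatment reduced opiate use during the treatment year. Section 1.2 makes reduced drug use the step through which HIV is prevented. Self-report does not fill the gap: Appendix I-A schedules the year 1 post-baseline risk assessment only at weeks 26 and 52.

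**Working it through.** The protocol states no sample size, power, attendance or expected missingness for this endpoint, so there is no figure to reproduce. The check has three parts.

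**1. How many year 1 urines are affected.** Four-weekly collection from week 4 to week 52 gives 52/4 = 13 times. Week 26 makes 14, or 13 if weeks 24 and 26 are combined, as 5.5 allows. Weeks 26 and 52 are full assessments in both arms. That leaves 14 - 2 = 12, or 13 - 2 = 11, urine times tied to counseling visits. The first, at about week 4, already falls after the 18 days of detoxification. A repeat detoxification could give some control participants a dispensing reason for a urine soon after week 26.

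**2. What selective attendance does.** Let p be the true opiate-positive share, and a+ and a- the chances that a positive or a negative participant gives a specimen. Then

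observed share = p·a+ / (p·a+ + (1-p)·a-).

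One pair of true shares follows from the Swedish buprenorphine trial as used in 7.4.2: substitution 1/20 + 19/20 × 0.20 = 0.240; detoxification 13/20 + 7/20 × 0.50 = 0.825. The value of 45% in the other pairs, the 70%, and all attendance rates are assumptions. Cells show the observed difference (detoxification minus substitution, percentage points), with bias in brackets.

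| Attendance a+/a- (%) | 24 v 82.5 (true 58.5) | 45 v 82.5 (true 37.5) | 45 v 70 (true 25.0) |
|---|---|---|---|
| (a) subst. 90/90, detox 70/70 | 58.5 (0) | 37.5 (0) | 25.0 (0) |
| (b) subst. 90/90, detox 60/90 | 51.9 (-6.6) | 30.9 (-6.6) | 15.9 (-9.1) |
| (c) subst. 60/95, detox 80/80 | 65.9 (+7.4) | 48.4 (+10.9) | 35.9 (+10.9) |
| (d) both arms 70/90 | 58.9 (+0.4) | 39.7 (+2.2) | 25.6 (+0.6) |
| (e) subst. 95/95, detox 85/95 | 56.8 (-1.7) | 35.8 (-1.7) | 22.6 (-2.4) |

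Example, (b) in the last column: detoxification 0.70 × 0.60 / (0.42 + 0.30 × 0.90) = 0.42/0.69 = 0.609, and 60.9 - 45.0 = 15.9. Example, (c) in the last column: substitution 0.45 × 0.60 / (0.27 + 0.55 × 0.95) = 0.27/0.7925 = 0.341, and 70.0 - 34.1 = 35.9.

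Unequal attendance alone (a) gives no bias. Dependence on drug use that is the same in both arms (d) gives little. The bias is material when that dependence differs by arm. An unweighted GEE with arm-by-visit terms and an independence working correlation returns these same observed shares, so it carries the same shift.

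**3. Two simple remedies, tested on 45 v 70 (true 25.0).**

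- Missing counted as positive: the difference is (1-p)·a- in substitution minus (1-p)·a- in detoxification. Case (a): 0.55 × 0.90 - 0.30 × 0.70 = 0.495 - 0.210 = 28.5 points. Case (b): 0.495 - 0.30 × 0.90 = 0.495 - 0.270 = 22.5 points. It can land above or below the truth, so it is not a bound.
- All randomized participants as denominator, with no value given to missing urines: these then count as negative. Case (b): 0.70 × 0.60 - 0.45 × 0.90 = 0.420 - 0.405 = 1.5 points. That is far worse than the 15.9 points from the specimens obtained.

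**The case against.** The strongest reply is that missing-data handling for a secondary endpoint normally sits in the analysis plan, which is not at hand, and that GEE approaches is a generic phrase that could include a weighted form. That is fair as far as missing detail goes, and no contradiction in the text is alleged. What remains is that the protocol does name the method, and that the method in its usual form, on this schedule, is exposed.

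A reader might infer more than the documents support:

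- **That only the substitution arm ever has a drug reason to attend.** Not so during the first 18 days or a repeat detoxification, and under 3.5.1 nobody receives BUP/NX after 52 weeks.
- **That the whole urinalysis comparison is compromised.** Urines at weeks 26, 52, 78, 104, 130 and 156 are scheduled alike in both arms.
- **That counseling is the only scheduled reason for controls to come.** ALT and bilirubin are drawn from everyone at weeks 12 and 40, and safety-phase participants in both arms have weekly assessments, including urine, in weeks 1 to 4.
- **That 155-160 against 45 to 60 visits shows fewer control urines.** These are scheduled visits, not attendance, and the urine schedule itself is the same.
- **That missing urines will bias the result.** No attendance data exist to show it, and case (a) shows that unequal missingness is not enough.

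The protocol also has mitigations: missed counseling and dispensing visits are pursued within a day (4.1), compensation is planned (8.5), and those who stop treatment are asked to stay in follow-up (3.5.1). These reduce the risk without removing it. Finally, 2.3 says the trial tests a prevention strategy, not the drug's efficacy for dependence, which limits the weight of this endpoint.

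**Conclusion.** The point holds as a risk confined to year 1, outside the initial detoxification, the week 26 and 52 assessments and any repeat detoxification. In that period most urines depend on counseling attendance, mainly one arm has a dispensing reason to attend, and the named comparison states no weighting or imputation.

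The size and direction of any bias are unknown. The span of -9.1 to +10.9 points comes from assumed attendance rates and, in part, assumed true shares. It shows what such mechanisms could do, not what will happen. It would need specimen-giving to depend on drug use in a way that differs by arm, which is plausible but not shown.

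The primary analysis of HIV infection or death is not affected. The change is worth making for a secondary endpoint because it is cheap and uses data already being collected.

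**What to change.** In Protocol 7.7.2 item 5:

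1. Report specimens obtained over specimens expected, by arm and visit.
2. Fit the repeated-measures comparison with inverse-probability-weighted GEE, or GEE after multiple imputation, using arm, attendance and earlier urine results. Both assume that specimens are missing at random given those variables, so neither corrects for current relapse that they do not capture.
3. For that reason add sensitivity analyses: missing counted as positive in both arms, and departures from missing at random that differ by arm. Label them as sensitivity analyses, not bounds.
4. Present the six-monthly urines as a separate comparison.
5. Do not use all randomized participants as the denominator unless missing urines are assigned a value.

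Visits, treatment and sample size stay as they are. The cost is revised analysis wording, modest programming and somewhat wider intervals.
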